## 5. SUBJECT ELIGIBILITY

To be eligible to participate in this study candidates must meet the following eligibility criteria within 28 days of Study Day 1 or at the time point specified in the individual eligibility criterion listed.

### 5.1. Inclusion Criteria

1. Must have given written informed consent (signed and dated) and any authorizations required by local law and be able to comply with all study requirements
2. Males or females aged 18–75 inclusive and weighing  $\geq 50$  kg at the time of informed consent
3. Satisfy the following:
  - a. Females: must be non-pregnant and non-lactating, and either:
    - i. surgically sterile (e.g., tubal occlusion, hysterectomy, bilateral salpingectomy, bilateral oophorectomy) or,
    - ii. post-menopausal (defined as 12 months of spontaneous amenorrhea in females  $> 55$  years of age or, in females  $\leq 55$  years, 12 months of spontaneous amenorrhea without an alternative medical cause and follicle stimulating hormone (FSH) levels in the postmenopausal range for the laboratory involved)
  - b. Males: Surgically sterile (i.e., bilateral orchidectomy) or abstinent\*, if engaged in sexual relations with a woman of child-bearing potential (WOCBP), the subject or subject's non-pregnant female partner must be using a highly effective contraceptive method from the time of signing the informed consent form until at least 13 weeks after the last dose of Study Drug (ISIS 757456 or placebo)

\* True abstinence (i.e., refraining from heterosexual intercourse throughout the duration of study participation) is only acceptable. Periodic abstinence (e.g., calendar, ovulation, symptothermal, post-ovulation methods), declaration of abstinence for the duration of a trial and withdrawal are not acceptable methods of contraception

4.  $BMI \leq 35.0 \text{ kg/m}^2$
5. Brachial circumference  $\geq 22$  and  $\leq 37$  cm (8.7 and 14.6 inches)
6. Subject must have been diagnosed with essential HTN for a minimum of 3 months prior to screening
7. At Screening, the subject must have a plasma AGT concentration  $\geq 20 \text{ } \mu\text{g/mL}$ . Up to 1 additional repeat test may be allowed in order to qualify with consultation of the Sponsor Medical Monitor
8. At Screening, the subject must have been on a stable regimen of 2 to 3 antihypertensive medications for at least 1 month prior to screening and will be required to maintain this regimen throughout the Study, using either an angiotensin-converting enzyme inhibitor (ACEi) or an angiotensin II receptor blocker (ARB), as well as 1 or 2 additional antihypertensive medications in the following categories:
  - a. beta blocker
    - i. acebutolol
    - ii. atenolol
    - iii. betaxolol
    - iv. bisoprolol
    - v. carvedilol
    - vi. labetalol
    - vii. metoprolol
    - viii. nadolol
    - ix. nebivolol
    - x. propranolol
    - xi. pindolol
  - b. calcium channel blocker or,
  - c. non-potassium sparing diuretic
9. At Screening and pre-dose Study Day 1, the average office seated BP must be within  $> 140 - \leq 170$  mmHg SBP and  $> 80$  mmHg DBP. The average is to be derived from 3 assessments taken within 10 minutes. Up to 2 additional tests at each time point is allowed in order to qualify.
10. Agree to abstain from alcoholic beverages for at least 24 hours prior to clinic visits
11. Agree to maintain adequate hydration and adhere to a low sodium diet throughout the study (from the Screening visit onward)

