**PROTOCOL SYNOPSIS (CONTINUED)**

Study Population (Continued)	Inclusion Criteria (Continued)
	
* True abstinence (i.e., refraining from heterosexual intercourse throughout the duration of study participation) is only acceptable. Periodic abstinence (e.g., calendar, ovulation, symptothermal, post-ovulation methods), declaration of abstinence for the duration of a trial and withdrawal are not acceptable methods of contraception
 
 
4. BMI <math>\leq</math> 35.0 kg/m^2
 
5. Brachial circumference <math>\geq</math> 22 and <math>\leq</math> 37 cm (8.7 and 14.6 inches)
 
6. Subject must have been diagnosed with essential hypertension (HTN) for a minimum of 3 months prior to screening
 
7. At Screening, the subject must have a plasma AGT concentration <math>\geq</math> 20 <math>\mu</math>g/mL. Up to 1 additional repeat test may be allowed in order to qualify with consultation of the Sponsor Medical Monitor
 
8. At Screening, the subject must have been on a stable regimen of 2 to 3 antihypertensive medications for at least 1 month prior to screening and will be required to maintain this regimen throughout the Study, using either an angiotensin-converting enzyme inhibitor (ACEi) or an angiotensin II receptor blocker (ARB), as well as one or two additional antihypertensive medications in the following categories: 
 
a. beta blocker 
 
i. acebutolol
 
ii. atenolol
 
iii. betaxolol
 
iv. bisoprolol
 
v. carvedilol
 
vi. labetalol
 
vii. metoprolol
 
viii. nadolol
 
ix. nebivolol
 
x. propranolol
 
xi. pindolol
 
 
 
b. calcium channel blocker or,
 
c. non-potassium sparing diuretic
 
 
 
9. At Screening and pre-dose Study Day 1, the average office seated blood pressure (BP) must be within <math>> 140 - \leq 170</math> mmHg SBP and <math>> 80</math> mmHg DBP. The average is to be derived from 3 assessments taken within 10 minutes. Up to 2 additional tests at each timepoint are allowed in order to qualify.
 
10. Agree to abstain from alcoholic beverages for at least 24 hours prior to clinic visits
 
11. Agree to maintain adequate hydration and adhere to a low sodium diet throughout the study (from the Screening Visit onward)
 

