### **4.2. Randomization**

Subjects will be randomized at Study Day 1, after all screening assessments have been completed and after the Investigator has verified that they are eligible per criteria in Section 5.1 and Section 5.2. No subject may begin treatment prior to randomization and assignment of a unique subject identification number.

Subjects will be stratified based on low Screening ACE/ARB dose or high Screening ACE/ARB dose (see Section 10.1 and Appendix E) and then subjects will be randomized 2:1 to receive ISIS 757456 or placebo as outlined in Section 3.1.

The Sponsor or designee will prepare the randomization list and utilize an automated IRT (Interactive Response Technology) system.

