## 5.2. Exclusion Criteria

1. Clinically significant abnormalities in medical history (e.g., previous acute coronary syndrome within 6 months of screening, major surgery within 3 months of screening, type I diabetes mellitus) or physical examination
2. History of secondary HTN
3. Subject with borderline orthostatic hypotension (assessed at Screening), when they assume a standing position (within 3 minutes of standing up), defined as:
  - a. A decrease in SBP of  $\geq 17$  mmHg or
  - b. A decrease in DBP of  $\geq 7$  mmHg
4. The use of the following at time of screening and during the course of the study:
  - a. Other medications for the treatment of HTN (e.g., clonidine, guanfacine, guanabenz, alpha-methyldopa, hydralazine, minoxidil, diazoxide, renin inhibitors)
  - b. Medications that may cause hyperkalemia (e.g., cyclosporine or tacrolimus, pentamidine, trimethoprim-sulfamethoxazole, all heparins)
  - c. Oral or SC anticoagulants (e.g., warfarin, rivaroxaban, apixaban, heparin, lovenox)
  - d. Organic nitrate preparations (e.g., nitroglycerin, isosorbide mononitrate, isosorbide dinitrate, or pentaerythritol)
  - e. Phosphodiesterase 5 inhibitors (e.g., sildenafil, tadalafil, vardenafil, avanafil)
  - f. Potassium sparing diuretics (e.g., eplerenone, spironolactone, amiloride, triamterene)
5. Treatment with another Study Drug, biological agent, or device within 1 month of screening, or 5 half-lives of study agent, whichever is longer
6. Previous treatment with an oligonucleotide or other RNA therapeutic (including siRNA) within 4 months of screening if single dose received, or within 12 months of screening if multiple doses received
7. Active infection with human immunodeficiency virus (HIV), hepatitis C (HCV) or hepatitis B (HBV) diagnosed by initial serological testing and confirmed with RNA testing, or prior treatment for hepatitis C. Patients at Screening who test positive by serology, but negative by RNA may be allowed in consultation with the Sponsor Medical Monitor
8. Malignancy within 5 years, except for basal or squamous cell carcinoma of the skin or carcinoma *in situ* of the cervix that has been successfully treated. Subjects with a history of other malignancies that have been treated with curative intent and which have no recurrence within 5 years may also be eligible if reviewed by the Sponsor Medical Monitor

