### BP Results

At the screening visit, measure the BP per instructions above with both the right and left arm. The arm with the highest BP (that meets inclusion/exclusion criteria) will be used at each subsequent visit.

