#### 8.6.5. Stopping Rules for Blood Pressure

1. In the event of a confirmed BP measurement  $\leq 90$  mmHg (systolic) and/or the subject remains symptomatic (i.e., dizziness, light-headedness, clammy skin, fatigue, blurry vision) after instituting oral or IV hydration, Study Drug should be permanently discontinued, and the subject should be referred to urgent care or the emergency room.

Any other antihypertensives or other medications that could affect BP should be stopped, if feasible. The use of IV angiotensin II or vasopressors should be considered in subjects that remain symptomatic and are hemodynamically unstable. The subject will continue to be followed per protocol in the study. Follow-up for subjects that screen fail due to BP inclusion criteria (see Section 5.1) will not be necessary.

2. Should a subject experience a BP measurement  $> 180$  mmHg (systolic) or  $> 110$  mmHg (diastolic) a second measurement must be done within a 30-minute period. If the subject then experiences a second BP measurement  $> 180$  mmHg (systolic) or  $> 110$  mmHg (diastolic), they will then be withdrawn from further blinded, randomized treatment. Study Drug is to be permanently discontinued unless the hypertensive event is transient and dependent on reversible initiating factors (e.g., stressful event). The suitability of the subject for continued dosing will be determined by the Investigator in consultation with the Sponsor Medical Monitor after the subject's BP has normalized. Additional antihypertensive medication(s) may be added per Investigator and Sponsor Medical Monitor judgement if the subject has discontinued Study Drug. If the subject has not discontinued Study Drug, changes to the stable regimen of antihypertensives may result in withdrawal of the subject from the Treatment Period. The subject will continue to be followed per protocol in the study. Follow-up for subjects that screen fail due to BP inclusion criteria (see Section 5.1) will not be necessary.

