**Table 7: Blood Pressure Monitoring and Stopping Rules Reference Table**

Confirmed Blood Pressure	Dosing	Additional Actions
SBP $\leq$ 90 mmHg* and/or subject is symptomatic (e.g., decreased oral intake, cold/flu, other illness).	Pause	Institute oral and/or IV hydration. If hypotension or symptoms of hypotension persist proceed to stopping rules below The suitability of the subject for continued dosing will be determined by the Investigator in consultation with the Sponsor Medical Monitor after the SBP has normalized and/or subject is no longer symptomatic and will be based on the reversibility of initiating factors (e.g., decreased oral intake, cold/flu, other illness)
SBP $\leq$ 90 mmHg* and/or the subject remains symptomatic after instituting oral and/or IV hydration and there is no other reason contributing to hypotensive event	Permanently Discontinue	The subject should be referred to urgent care or the emergency room Any other antihypertensives or other medications that could affect BP should be stopped, if feasible The use of IV angiotensin II or vasopressors should be considered in subjects that remain symptomatic and are hemodynamically unstable The subject will continue to be followed per protocol in the study. Follow-up for subjects that screen fail due to BP inclusion criteria (see Section 5.1) will not be necessary
SBP $>$ 180 mmHg* or DBP $>$ 110 mmHg*	Pause if BP elevation is thought to be transient, reversible and related to external initiating factors (e.g., stressful event) Permanently discontinue if no other reason contributing to hypertensive event	The suitability of the subject for continued dosing will be determined by the Investigator in consultation with the Sponsor Medical Monitor after the subject's BP has normalized Additional antihypertensive medication(s) may be added per Investigator and Sponsor Medical Monitor judgement if the subject has discontinued Study Drug. If the subject has not discontinued Study Drug, changes to the stable regimen of antihypertensives may result in withdrawal of the subject from the Treatment Period The subject will continue to be followed per protocol in the study. Follow-up for subjects that screen fail due to BP inclusion criteria (see Section 5.1) will not be necessary

\* BP measurements must be confirmed by a second measurement within 30 minutes

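### Inclusion 9 caps systolic but not diastolic pressure, so a subject with sustained DBP above the 110 mmHg stopping threshold passes every numeric blood-pressure entry criterion

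*Combined protocol and SAP*

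**What the plan says.** **Entry.** Protocol Section 5.1, item 9, begins "At Screening and pre-dose Study Day 1, the average office seated BP must be within" limits, and the synopsis has the same criterion ("At Screening and pre-dose Study Day 1, the average office seated blood pressure (BP) must be within"). In both places SBP has a floor and a ceiling (above 140, at most 170 mmHg), while DBP has a floor only (above 80 mmHg). The value is a mean of three readings, with up to two further tests at each time point. Section 5.2 contains no numeric DBP limit.

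**Choice of arm.** Under BP Results in Section 6.1.1.1, "The arm with the highest BP (that meets inclusion/exclusion criteria) will be used at each subsequent visit".

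**Check before randomization.** Section 4.2 randomizes subjects "after the Investigator has verified that they are eligible per criteria in Section 5.1 and Section 5.2".

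**Stopping.** Section 8.6.5(2) applies when SBP exceeds 180 or DBP exceeds 110 mmHg and a second measurement within 30 minutes agrees. Subjects meeting it: "they will then be withdrawn from further blinded, randomized treatment". It adds: "Study Drug is to be permanently discontinued unless the hypertensive event is transient and dependent on reversible initiating factors". Table 7 allows a pause for a transient, externally caused rise, and otherwise says "Permanently discontinue if no other reason contributing to hypertensive event". Neither place makes an allowance for a subject whose baseline pressure was already above the threshold.

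**The concern.** Entry criteria and stopping rules should not contradict each other. Here the numeric entry criteria admit a pressure that the same protocol treats as a reason to take a subject off Study Drug.

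The subject in question would be asked to keep an unchanged antihypertensive regimen (Section 8.2). A change to it may lead to withdrawal from treatment (Section 8.10.1). With 2:1 randomization the chance of placebo is 1 in 3. Whether such a person enters is left to each site's judgment in a multicenter trial, although the equivalent SBP question is settled by a number.

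There is a secondary analytic cost. A subject stopped early may receive fewer than 7 of the 9 doses and so drop out of the Per Protocol Set, on which the primary analysis is run.

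**Working it through.** The plan states no figure to reproduce. The check compares two sets of blood-pressure values.

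**1. The two regions**

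| | Entry (inclusion 9) | Stop (8.6.5(2), Table 7) | Gap |
|---|---|---|---|
| SBP | > 140 to ≤ 170 | > 180 | 180 − 170 = 10 mmHg |
| DBP | > 80, no upper limit | > 110 | none; regions overlap |

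The stop needs either limb, not both. The overlap is therefore SBP > 140 to ≤ 170 with DBP > 110. A sustained 160/112 mmHg lies in it.

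**2. Does the difference in measurement remove the overlap?** Entry uses a mean of three readings; the stop uses a measurement and a repeat within 30 minutes. With a sustained DBP above 110 both are met. For a subject near 110 the two can disagree, so the overlap is clear-cut only for sustained values.

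**3. Does the exception remove it?** The exception covers transient events with reversible causes. A DBP above 110 at both Screening and Day 1 does not look transient.

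**4. Do other provisions remove it?**
- Section 4.2 verifies eligibility, but against numeric criteria that this subject passes.
- Section 6.1.1.1 selects the arm by reference to the same criteria, so an arm above 110 diastolic qualifies.
- Exclusion 1 ("Clinically significant abnormalities in medical history" or on examination), exclusion 15 (clinically significant examination findings) and exclusion 18 (unsuitability, or likely interference with taking part or finishing) could each apply. None carries a DBP number.
- Section 6.1.2 and Appendix A, footnote 2, call for pressure or vital signs to be reviewed before dosing, again without a separate DBP limit.

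The remaining barriers all depend on judgment.

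**5. How wide is the overlap?** It needs a pulse pressure below 170 − 110 = 60 mmHg. The documents give no distribution of DBP in the target population, so no frequency can be computed.

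**6. Consequence for the primary analysis.** Doses fall on Days 1, 3, 8, 15, 22, 29, 36, 43 and 50 (Section 3.4.2). The seventh is Day 36, so a stop at or before the Day 36 pre-dose check leaves at most 6 doses and removes the subject from the Per Protocol Set. Assume a 20:10 split and equal variances; the standard error of the treatment difference is then proportional to √(1/n₁ + 1/n₂):
- one active subject lost: √(1/19 + 1/10) / √(1/20 + 1/10) = 0.3907 / 0.3873 = 1.009, a rise of 0.9%;
- one placebo subject lost: √(1/20 + 1/9) / √(1/20 + 1/10) = 0.4014 / 0.3873 = 1.036, a rise of 3.6%.

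**7. Effect of a ceiling.** With DBP ≤ 110 at entry, the mean that qualifies a subject can no longer lie in the stopping region. The gap is then 110 − 110 = 0 mmHg: no overlap on means, and no margin.

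**The case against.** The best reply is that eligibility means satisfying both Sections 5.1 and 5.2, and exclusion 18 is a formal criterion. A subject already above the protocol's own stopping threshold fits its second limb closely, because that pressure could well prevent completion. A sensible investigator would exclude such a person. This stands. A reader might infer that the protocol obliges sites to enroll the subject, or that nothing prevents entry; the documents support neither. What they support is narrower: the numeric criteria are passed, and exclusion depends on judgment.

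A reader might also infer that the stopping rule is triggered at baseline. The rule ends further blinded treatment, so before the first dose the subject exceeds the threshold without having met the rule. If it were instead read as applying on Day 1, the pre-dose review would block the first dose, which gives a written safeguard. On the narrower reading the next scheduled pressure check is Day 3, then weekly, and antihypertensives may be added once Study Drug is stopped. So there is an early backstop either way, but it works by stopping a subject who need not have been entered.

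Finally, the protocol states no principle that entry limits must sit a fixed distance below stops. Some other limits do leave a margin: potassium is 4.9 mmol/L at entry against a hold at 5.5, and the orthostatic fall is 17/7 at entry against 20/10 mmHg on study. The orthostatic figure is a diagnostic definition, however, not a dosing stop. These comparisons make an oversight plausible but do not prove one. They do not justify insisting on a 10 mmHg diastolic margin.

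**Conclusion.** The gap is real and small. Inclusion 9 limits SBP to 10 mmHg below its stop and leaves DBP uncapped, so a sustained DBP above 110 with SBP above 140 and at most 170 mmHg passes all numeric entry criteria while exceeding the stopping threshold. This follows from the text alone.

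Three things limit its weight. Frequency is unknown and probably low. Judgment-based provisions would often keep the subject out. The effect on the angiotensinogen comparison is small: 0.9% to 3.6% on the standard error per subject lost, under the assumed 20:10 split, with follow-up continuing after a stop and a Full Analysis Set summary planned in SAP Section 3.3.1.

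A reader might want to put a probability on such a subject being stopped before the seventh dose. The documents give no within-subject variability, between-visit correlation or expected drug effect on DBP, so no such figure is supported. It is enough that a sustained DBP above 110 faces withdrawal at the first confirmed on-treatment reading.

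The case rests on subject safety and consistent rules. Low severity; a cheap improvement.

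**What to change.** In Section 5.1, item 9, and in the synopsis, change the diastolic condition to > 80 to ≤ 110 mmHg, at both Screening and pre-dose Day 1. Exclusions 1, 15 and 18 stay as they are.

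This removes the overlap on mean values. It does not guarantee that a subject near 110 will never have a confirmed reading above it. A lower ceiling is optional for the sponsor: ≤ 100 mmHg would match the 10 mmHg systolic gap, but symmetry is its only support and it would exclude more subjects.

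The cost is one line in two places and, at ≤ 110 mmHg, probably very few otherwise eligible subjects. No analysis or visit schedule changes.

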## 5.2. Exclusion Criteria

1. Clinically significant abnormalities in medical history (e.g., previous acute coronary syndrome within 6 months of screening, major surgery within 3 months of screening, type I diabetes mellitus) or physical examination
2. History of secondary HTN
3. Subject with borderline orthostatic hypotension (assessed at Screening), when they assume a standing position (within 3 minutes of standing up), defined as:
  - a. A decrease in SBP of  $\geq 17$  mmHg or
  - b. A decrease in DBP of  $\geq 7$  mmHg
4. The use of the following at time of screening and during the course of the study:
  - a. Other medications for the treatment of HTN (e.g., clonidine, guanfacine, guanabenz, alpha-methyldopa, hydralazine, minoxidil, diazoxide, renin inhibitors)
  - b. Medications that may cause hyperkalemia (e.g., cyclosporine or tacrolimus, pentamidine, trimethoprim-sulfamethoxazole, all heparins)
  - c. Oral or SC anticoagulants (e.g., warfarin, rivaroxaban, apixaban, heparin, lovenox)
  - d. Organic nitrate preparations (e.g., nitroglycerin, isosorbide mononitrate, isosorbide dinitrate, or pentaerythritol)
  - e. Phosphodiesterase 5 inhibitors (e.g., sildenafil, tadalafil, vardenafil, avanafil)
  - f. Potassium sparing diuretics (e.g., eplerenone, spironolactone, amiloride, triamterene)
5. Treatment with another Study Drug, biological agent, or device within 1 month of screening, or 5 half-lives of study agent, whichever is longer
6. Previous treatment with an oligonucleotide or other RNA therapeutic (including siRNA) within 4 months of screening if single dose received, or within 12 months of screening if multiple doses received
7. Active infection with human immunodeficiency virus (HIV), hepatitis C (HCV) or hepatitis B (HBV) diagnosed by initial serological testing and confirmed with RNA testing, or prior treatment for hepatitis C. Patients at Screening who test positive by serology, but negative by RNA may be allowed in consultation with the Sponsor Medical Monitor
8. Malignancy within 5 years, except for basal or squamous cell carcinoma of the skin or carcinoma *in situ* of the cervix that has been successfully treated. Subjects with a history of other malignancies that have been treated with curative intent and which have no recurrence within 5 years may also be eligible if reviewed by the Sponsor Medical Monitor
9. History of bleeding diathesis, coagulopathy, immune thrombocytopenic purpura, thrombotic cytopenic purpura, or any qualitative or quantitative platelet defect
10. Recent history of, or current drug or alcohol abuse
11. Unstable/underlying cardiovascular disease defined as:
  - a. Any history of congestive heart failure (NYHA class II-IV)

- b. Any history of previous stroke, transient ischemic attack, unstable or stable angina pectoris, or myocardial infarction prior to screening
  - c. 12-lead ECG demonstrating a QT interval (corrected using Fridericia's formula [QTcF]) > 450 msec in males and > 470 msec in females at Screening, or a history or evidence of long QT syndrome
  - d. Any clinically significant active atrial or ventricular arrhythmias
  - e. Any history of coronary bypass or percutaneous coronary intervention
12. Active infection requiring systemic antiviral or antimicrobial therapy that will not be completed prior to Study Day 1
  13. Show evidence of uncorrected hypothyroidism or hyperthyroidism hormone results at Screening. Subjects receiving dose-stable thyroid replacement therapy for at least 3 months prior to screening will be allowed to participate as long as thyroid tests (TSH/T3/T4) show that subject is euthyroid
  14. Screening laboratory results as follows, or any other clinically significant abnormalities in screening laboratory values that would render a subject unsuitable for inclusion
    - a. Urine protein/creatinine (P/C) ratio  $\geq 0.3$  mg/mg. In the event of P/C ratio above this threshold eligibility may be confirmed by a quantitative total urine protein measurement of < 300 mg/24 hr
    - b. Positive test (including trace) for blood on urinalysis. In the event of a positive test eligibility may be confirmed with urine microscopy showing  $\leq 5$  red blood cells per high power field
    - c. Alanine aminotransferase (ALT), aspartate aminotransferase, bilirubin, alkaline phosphatase (ALP), serum creatinine, blood urea nitrogen (BUN) > 1.5 x upper limit of normal (ULN)
    - d. Platelet count < lower limit of normal (LLN)
    - e. Serum potassium > 4.9 mmol/L
    - f. Estimated glomerular filtration rate (eGFR) of < 45 mL/min/1.73 m^2 using the CKD Epidemiology Collaboration formula
  15. Clinically significant abnormalities upon physical examination which in the Investigator's opinion should exclude the subject from study participation
  16. Subject works night time shifts (e.g., 11 PM to 7 AM)
  17. Blood donation of 50 to 499 mL within 30 days of screening or of > 499 mL within 60 days of screening
  18. Have any other conditions, which, in the opinion of the Investigator or Sponsor would make the subject unsuitable for inclusion, or could interfere with the subject participating in or completing the study
  19. Unwilling to comply with study procedures, including the Post-Treatment Period, as specified by this protocol, or unwillingness to cooperate fully with the Investigator

